**Table 12: Dose Adjustment for QTc Interval Prolongation**

Formatted: C-Hyperlink

Formatted: C-Hyperlink

For all QTc interval prolongations (average of the triplicate 12-lead readings or by Holter):  
Check serum electrolyte levels (including magnesium, potassium, and calcium) and correct any abnormalities. If possible, stop any medications that may prolong the QTc interval.

Subjects who experience Grade <math>\geq 2</math> QTcF prolongation and undergo dose interruption and/or reduction must be monitored closely with ECGs, performed twice weekly for the first week of the QTcF prolongation and then weekly thereafter until the QTcF prolongation is resolved.
	
Grade 2: QTcF (average of triplicate ECG readings) $> 480\text{ms}$ and $\leq 500\text{ms}$	Reduce the dosage of one dose level without interrupt the administration  To resume the treatment at the previous dose level if the QTcF has decreased to within 30 ms of baseline or $< 450\text{ ms}$
Grade 3: QTcF (average of triplicate ECG readings) $> 500\text{ms}$ for the first time; $> 60\text{ ms}$ change from baseline	Interrupt DS-1594b administration. If QTcF returns to within 30 ms of baseline or $< 450\text{ ms}$ within 14 days, study drug administration may be resumed at ONE dose level below the current dose.
QTcF (average of triplicate ECG readings) $> 500\text{ms}$ repeatedly	Permanently discontinue DS-1594b administration if QTcF recurs despite appropriate dose reduction and correction/elimination of other risk factors (eg serum electrolyte abnormalities, discontinuation of a concomitantly administered drug susceptible to prolong QT)
Grade 4: Torsade de pointes or polymorphic ventricular tachycardia or signs/symptoms of serious arrhythmia	Permanently discontinue DS-1594b administration

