#### 4.2. **Exclusion Criteria**

- a. Subjects with a known allergy, hypersensitivity, or contraindication to the protocol therapies or any of their components to be used in the arm the subject is to be enrolled on.
- b. Uncontrolled or significant cardiovascular disease, including any of the following:
  - Bradycardia of less than 50 beats per minute, unless the subject has a pacemaker;
  - QTcF interval >450 msec;
  - Diagnosis of or suspicion of long QT syndrome (including family history of long QT syndrome);
  - Systolic blood pressure  $\geq$ 180 mmHg or diastolic blood pressure  $\geq$ 110 mmHg;
  - History of clinically relevant ventricular arrhythmias within 6 months prior to screening (eg, ventricular tachycardia, ventricular fibrillation, or Torsade de Pointes);
  - History of second (Mobitz II) or third-degree heart block (subjects with pacemakers are eligible if they have no history of fainting or clinically relevant arrhythmias while using the pacemaker);
  - History of uncontrolled angina pectoris, unstable angina or myocardial infarction, CABG, CVA, TIA, symptomatic pulmonary emboli within 6 months prior to Screening;
  - New York Heart Association Class 3 or 4 heart failure;
  - Left ventricular ejection fraction (LVEF)  $\leq$ 50 or less than the institutional lower limit of normal;
  - Complete left bundle branch block (right bundle branch block is permitted, but requires manual reading of the QTc interval);
  - Active cardiac dysrhythmias of NCI CTCAE grade  $\geq$  2 (eg, atrial fibrillation).
- c. Persisting toxicity related to prior therapy of Grade  $>$ 1 NCI-CTCAE v 5.0; however, alopecia and sensory neuropathy Grade 2 or lower is acceptable
- d. Underwent HSCT within 90 days of the first dose of protocol therapy, or subjects with clinically significant (Grade 2 or greater) graft-versus-host disease (GVHD) (the use of topical steroids for ongoing cutaneous GVHD is permitted)
- e. Subjects with symptomatic CNS leukemia or subjects with poorly controlled CNS leukemia.
- f. Active and uncontrolled disease (active infection requiring systemic therapy, fever likely secondary to infection within prior 48 hours, uncontrolled hypertension despite adequate medical therapy as judged by the treating physician).
- g. Active (uncontrolled, metastatic) other malignancies
- h. Major surgery within 28 days prior to the first dose of protocol therapy

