### 6.2.3. DS-1594b AEs of Special interest

#### 6.2.3.1. QTc Prolongation, Torsade de Pointes, and Other Ventricular Arrhythmias

Subjects who experience >480 ms QTcF prolongation and undergo dose interruption and/or reduction must be monitored closely with ECGs, performed twice weekly for the first week of the QTcF prolongation and then weekly thereafter until the QTcF prolongation is resolved ([Table 12](#)  
[Table 12](#)).

Formatted: C-Hyperlink

QTcF prolongation of Grade 3 or higher, either serious or non-serious and whether or not causally related, must be recorded as AE or SAE in the Electronic Data Capture (EDC) system within 24 hours of awareness of the central ECG laboratory reading, with the investigator's assessment of seriousness, causality, and a detailed narrative. The central ECG reading confirming QTcF prolongation  $\geq$  Grade 3 is to be recorded in the EDC system.

Regarding the detailed narrative(s):

- Serious AESI: The narrative will be captured directly in the EDC system.
- Non-Serious AESI: The narrative will be captured on a form outside of the EDC system (paper form).

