#### **6.2.4. Management of AESI**

##### **6.2.4.1. QTc Prolongation, TdP, and Other Ventricular Arrhythmias**

Electrolytes (potassium, calcium, and magnesium) should be checked and supplementation given to correct any values outside the normal range.

Concomitant medications should be reviewed to identify and, if appropriate, discontinue any medication with known QT prolonging effects ([Table 28](#)[Table 28](#)).

Formatted: C-Hyperlink

Subjects who experience >480 msec QTcF prolongation and undergo dose interruption and/or reduction must be monitored closely with ECGs, performed twice weekly for the first week of the QTcF prolongation and then weekly thereafter until the QTcF prolongation is resolved.

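### Table 12 does not say how its two Grade 3 QTcF conditions combine, and each reading leaves a conflict or a gap; Sections 6.2.3.1 and 6.2.4.1 also state the ECG follow-up trigger differently

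*Combined protocol and SAP*

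**What the plan says.** All of this is in the combined protocol and SAP.

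- **Table 12, Grade 2 row** (average triplicate QTcF above 480 and up to 500 ms): "Reduce the dosage of one dose level without interrupt the administration".
- **Table 12, Grade 3 row**: QTcF above 500 ms "for the first time; $> 60\text{ ms}$ change from baseline". No 'and' or 'or' joins the two conditions. The action is "Interrupt DS-1594b administration. If QTcF returns to within 30 ms of baseline or" below 450 ms "within 14 days, study drug administration may be resumed at ONE dose level below the current dose".
- **Table 12, other rows**: repeated values above 500 ms, and Grade 4 arrhythmia.
- **Table 12, follow-up rule**: keyed to Grade 2 or higher "QTcF prolongation and undergo dose interruption and/or reduction must be monitored closely with ECGs, performed twice weekly for the first week", then weekly until resolution.
- **Section 6.2.3.1**: "Subjects who experience >480 ms QTcF prolongation and undergo dose interruption and/or reduction must be monitored closely with ECGs", on the same schedule and with a reference to Table 12.
- **Section 6.2.4.1**: "Subjects who experience >480 msec QTcF prolongation and undergo dose interruption and/or reduction must be monitored closely with ECGs", on the same schedule.
- **Section 4.2** excludes "QTcF interval >450 msec", so QTcF at screening is at most 450 ms.
- **Section 8.4.1** triggers an unscheduled PK sample on a change above 60 msec or a new absolute QTcF of at least 500 msec, with the 'or' printed. **Section 9.4.7.4** tabulates absolute values and changes from baseline as separate categories.

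**The concern.** A dose-adjustment table should send each ECG result to exactly one row, and a result that requires interruption should not already satisfy the condition for restarting. Table 12 mixes absolute and baseline-relative limits without saying how they combine, so neither property is assured. The follow-up rule is then repeated in two other sections with a trigger that has no baseline-relative part.

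This matters more than an ordinary drafting slip because it concerns QT. Section 7.2 says this is the first clinical study of the drug. Section 2.4.2 reports potent hERG activity and dose-dependent QTc prolongation in monkeys. Section 3.1 gives QT risk as a reason for twice-daily dosing. QTcF prolongation of Grade 3 or higher is an adverse event of special interest (Section 8.10.2). Two investigators reading the same page could manage the same ECG differently.

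**Working it through.** The plan states no figure on this point to reproduce. The check is whether the thresholds are consistent with one another.

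**Notation.** B is baseline QTcF and Q is on-treatment QTcF, both in ms. The resume condition is Q − B ≤ 30 or Q < 450. The Grade 2 row is 480 < Q ≤ 500.

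**Reading 1: either condition is enough** (Q > 500 or Q − B > 60).

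1. *Interrupt and resume together.* This needs B + 60 < Q < 450, so B < 390. Example: B = 385, Q = 446. The change is 446 − 385 = 61 > 60, so interrupt; 446 < 450, so the resume condition is already met. The baseline-relative part of the resume condition is not met (61 > 30), and the absolute part bypasses it. In whole milliseconds the highest affected baseline is 388 (388 + 61 = 449).
2. *Source of the overlap.* A rise above 60 cannot also be a rise of at most 30. Q > 500 with Q − B ≤ 30 would need B > 470, above the entry limit of 450. The whole overlap therefore comes from the alternative of being below 450 ms.
3. *Two rows at once.* This needs 480 < Q ≤ 500 and Q > B + 60, so B < 440. Example: B = 420, Q = 485, change +65. The Grade 2 row says reduce without interrupting; the Grade 3 row says interrupt.
4. *Follow-up trigger.* A Grade 3 event with Q ≤ 480 needs B + 60 < 480, so B < 420. Example: B = 400, Q = 465, change +65. It is inside the Table 12 follow-up rule and outside the trigger in 6.2.3.1 and 6.2.4.1.

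**Reading 2: both conditions are required** (Q > 500 and Q − B > 60).

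5. Every Grade 3 event now exceeds 500 ms, so items 1, 3 and 4 disappear.
6. *No row at all.* A first value with Q > 500 and Q − B ≤ 60 needs B > 440. Example: B = 445, Q = 503, change +58. It is too high for Grade 2, fails the second Grade 3 condition, and is not a repeat.

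**Enumeration as a check.** Whole-millisecond pairs, B from 340 to 450 (upper end from the entry limit, lower end assumed) and Q from B to 560:

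| Condition | Either | Both |
|---|---|---|
| Interrupt and resume both met | 1225 | 0 |
| Grade 2 and Grade 3 rows both met | 1810 | 0 |
| Grade 3 with Q ≤ 480 | 3240 | 0 |
| First Q > 500 in no row | 0 | 55 |

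These counts show only where conflicts exist. They depend on the assumed grid and are not probabilities.

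**The case against.** The strongest reply has four parts.

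**The overlap rests on reading the semicolon as 'or'.** This is correct, and Table 12 does not say so; cell layout may also have been lost in the PDF. Sections 8.4.1 and 9.4.7.4 treat the two limits separately, which favours 'or', but they govern PK sampling and tabulation. Reading it as 'and' does not rescue the table, because item 6 then applies.

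**Returning to a value implies a later ECG.** That is a fair reading of the verb. But the subject in item 1 was never at or above 450 ms, so the absolute part of the condition is either already met or has no clear meaning.

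**The resume rule already refers to baseline, and resumption is optional and one dose level lower.** Both statements stand. A reader might infer that resumption ignores the change from baseline, or that the event has no consequence. The text supports neither: a 30 ms criterion exists, though it can be bypassed, and a dose reduction remains.

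**Follow-up is not missing.** This also stands. A reader might infer that a Grade 3 event can go without follow-up ECGs. Table 12 requires them for every Grade 2 or higher event with interruption or reduction. Sections 6.2.3.1 and 6.2.4.1 do not release anyone from that, and 480 ms may be shorthand for the Grade 2 lower limit. Scheduled triplicate ECGs continue as well (Tables 20 and 21). What remains is a mismatch of wording.

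**Conclusion.** Table 12 needs correction whichever way its Grade 3 row is read. As alternatives, the two conditions let one ECG require interruption and already meet the resume condition (baseline below 390 ms), and let one ECG fall under two rows with different actions (baseline below 440 ms). As joint requirements, they leave a first value above 500 ms without a row (baseline above 440 ms). The difference between Table 12 and Sections 6.2.3.1 and 6.2.4.1 is an inconsistency, not a gap in required monitoring. For Grade 3 events it arises only on the 'or' reading, with baseline below 420 ms.

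A reader might also infer that DLT counts are affected. The documents do not establish this: Section 3.2.2 keys the DLT to CTCAE Grade 3 QTcF prolongation and does not cite Table 12. It would follow only if Table 12's wording were used for grading.

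The point is moderate. The ranges assume baselines of at most 450 ms; the entry limit applies at screening, while Section 9.4.2 defines baseline as the last value before first dose, which may differ. The documents do not give the distribution of baseline QTcF, so the number of subjects affected cannot be estimated.

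**What to change.** 1. State in the Grade 3 row of Table 12 how the two conditions combine.
2. Reconcile Table 12 with Sections 6.2.3.1 and 6.2.4.1 so that one event definition drives interruption, follow-up ECGs and resumption.
3. Before finalising, test the revised rows over the plausible range of baseline and on-treatment values. No pair should fall in two rows, a value above the lowest action limit should not fall in none, and no pair should meet the interruption and resumption conditions together.

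The thresholds and actions are for the sponsor's clinical team to set; none is proposed here. The cost is amendment wording in one table and two sections, and possibly a few more follow-up ECGs in subjects who already had an event. The sample size and statistical analysis do not change.

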**Table 13: Dose Modification for Clinically Suspected Acute Differentiation Syndrome**

Occurrence	Action	DS-1594b dose modification
1st	Interrupt If severe pulmonary symptoms (requiring intubation or ventilatory support), and/or renal dysfunction persisting more than 48 hours after initiation of corticosteroids Resume when until signs and symptoms no longer severe (i.e. improve to Grade 2* or lower); Start treatment with systemic corticosteroids	If signs and symptoms improve to Grade 2* or lower within 7 days, resume at ONE dose level below current dose.  Escalate back to current dose after 7 days, if the reduced dose is tolerated after.  If syndrome persists for $\geq 7$ days despite supportive management, discontinue permanently.
2nd	Discontinue DS-1594b permanently; start systemic corticosteroid treatment	Not applicable.

\*Grade 1 is mild, Grade 2 is moderate, Grade 3 is serious, Grade 4 is life-threatening.

### 6.2.3. DS-1594b AEs of Special interest

#### 6.2.3.1. QTc Prolongation, Torsade de Pointes, and Other Ventricular Arrhythmias

Subjects who experience >480 ms QTcF prolongation and undergo dose interruption and/or reduction must be monitored closely with ECGs, performed twice weekly for the first week of the QTcF prolongation and then weekly thereafter until the QTcF prolongation is resolved ([Table 12](#)  
[Table 12](#)).

Formatted: C-Hyperlink

QTcF prolongation of Grade 3 or higher, either serious or non-serious and whether or not causally related, must be recorded as AE or SAE in the Electronic Data Capture (EDC) system within 24 hours of awareness of the central ECG laboratory reading, with the investigator's assessment of seriousness, causality, and a detailed narrative. The central ECG reading confirming QTcF prolongation  $\geq$  Grade 3 is to be recorded in the EDC system.

Regarding the detailed narrative(s):

- Serious AESI: The narrative will be captured directly in the EDC system.
- Non-Serious AESI: The narrative will be captured on a form outside of the EDC system (paper form).

#### 6.2.3.2. Combined Elevations of Aminotransferases and Bilirubin

Combined elevations of aminotransferases and bilirubin, either serious or non-serious and whether or not causally related, meeting the laboratory criteria of a potential Hy's Law case [ALT or AST  $\geq 3 \times$  ULN with simultaneous TBL  $\geq 2 \times$  ULN] should always be recorded as an AE or SAE within 24 hours of awareness, with the investigator's assessment of seriousness, causality, and a detailed narrative.

Regarding the detailed narrative(s):

- Serious AESI: The narrative will be captured directly in the EDC system.
- Non-Serious AESI: The narrative will be captured on a form outside of the EDC system (paper form).

For liver elevation, workup elevations meeting FDA DILI criteria below:

Elevation of liver enzymes that meet the criteria below should be investigated and the cause identified when possible:

- ALT  $>8 \times$  ULN; or
- AST or ALT  $>5 \times$  ULN for more than two weeks; or
- ALT or AST  $>3 \times$  ULN, but not reaching the limits in the above criteria, in combination with clinical symptoms suggestive of hepatitis; or
- ALT or AST  $>3 \times$  ULN with TBL  $>2 \times$  ULN.

Once the cause of liver enzyme elevation is identified, remove or treat the contributing cause.

If the above criteria are met and the elevation is considered to be related or possibly related to DS-1594b, dosing should be interrupted.

Liver enzyme level testing will be repeated at least weekly, or more frequently, based on degree of hepatic laboratory abnormality. If the liver enzyme levels return to baseline levels, DS-1594b may be resumed at ONE dose level below the current dose level. If toxicity does not improve/resolve within 28 days, then DS-1594b will be discontinued. Upon resumption of DS-1594b, if liver enzyme elevations recur, treatment must be permanently discontinued.

#### **6.2.4. Management of AESI**

##### **6.2.4.1. QTc Prolongation, TdP, and Other Ventricular Arrhythmias**

Electrolytes (potassium, calcium, and magnesium) should be checked and supplementation given to correct any values outside the normal range.

Concomitant medications should be reviewed to identify and, if appropriate, discontinue any medication with known QT prolonging effects ([Table 28](#)[Table 28](#)).

Formatted: C-Hyperlink

Subjects who experience >480 msec QTcF prolongation and undergo dose interruption and/or reduction must be monitored closely with ECGs, performed twice weekly for the first week of the QTcF prolongation and then weekly thereafter until the QTcF prolongation is resolved.

##### **6.2.4.2. Combined Elevations of Aminotransferases and Bilirubin**

Combined elevations of aminotransferases and bilirubin, either serious or non-serious and whether or not causally related, meeting the laboratory criteria of a potential Hy's Law case [ALT or AST  $\geq 3$  x ULN with simultaneous TBL  $\geq 2$  x ULN] should always be recorded as an AE or SAE within 24 hours of awareness, with the Investigator's assessment of seriousness, causality, and a detailed narrative. Subjects will be monitored as described in Section 8.10. Evaluation may include the following depending on the clinical situation:

- Medical history and physical exam, including focus on medications and substances used: alcohol, acetaminophen, azole antifungals, change in medication dosages, new medications added, over the counter medication use and recreational drug use. Check for change in diet or use of dietary supplements;
- Abdominal ultrasound;
- Hepatitis A, B, C, and E screening (anti-hepatitis A virus immunoglobulin M, hepatitis B surface antigen, anti-hepatitis C virus plus viral titer, and evaluation for Hepatitis E), antinuclear antibody and anti-Smith antibody, cytomegalovirus, Epstein Barr virus;
- Additional evaluations as deemed appropriate by the Investigator to exclude other causes of liver enzyme and bilirubin elevations;
- All laboratory results, including local laboratory reference ranges are to be recorded.

### **6.3. CYP3A and P-gp Inhibitors: Dose modifications Venetoclax**

Venetoclax should be administered at 50% dose reduction in the setting of moderate CYP3A inhibitor and at 75% dose reduction in the setting of strong CYP3A inhibitor for the duration of co-administration. The venetoclax dose will be reduced to 70mg by mouth once daily if subject is on posaconazole.

In the event the co-administered CYP3A inhibitor is discontinued, the assigned venetoclax dose should be resumed 3 days after discontinuation.

Every effort should be made to adhere venetoclax dose reduction. Variations in schedule of events such as late/missed interventions that do not affect the rights and safety of the subject will not be considered as deviations.

P-gp substrates: Concomitant use of venetoclax increases Cmax and AUCinf of P-gp substrates, which may increase toxicities of these substrates (please see Venetoclax US prescribing information). Avoid concomitant use of venetoclax with a P-gp substrate. If a concomitant use is unavoidable, separate dosing of the P-gp substrate at least 6 hours before venetoclax.

### **6.4. Tumor Lysis Prophylaxis (TLS)**

The venetoclax dose titration scheme utilized in the AML studies performed to date to mitigate the risk of Tumor Lysis Syndrome (TLS) will be employed. All subjects will be hospitalized for the entirety of the venetoclax dose escalation starting at least on Day 1 of treatment initiation and until 24 hours after the completion of venetoclax dose escalation. During Cycle 1, venetoclax will be dose escalated daily to the goal dose regimen of 400 mg daily. Subjects will receive 100 mg on Day 1, 200 mg on Day 2, and 400 mg on Day 3 and onwards, or adjusted dose if on concomitant azoles (discussed below in Section 6.7).

To mitigate the risk for TLS, subjects must be receiving tumor lysis prophylaxis, including hydration (oral, intravenous) and treatment with a uric acid reducing agent (allopurinol, rasburicase) prior to start of venetoclax and at least during the first cycle of therapy.

TLS chemistry tests (potassium, uric acid, creatinine, calcium and phosphorus) will be obtained prior to dosing and 5 to 8 hours after each day of a new venetoclax dose. TLS chemistry test results will be reviewed by the investigator in real time and prior to the subject's next dose to ensure appropriate management. If a subject meets the criteria for clinically significant laboratory or clinical TLS, no additional venetoclax should be administered until resolution. Venetoclax interruption for up to 72 hours following transient (< 48 hours) chemical changes and laboratory TLS will be allowed and will not require a dose reduction.

### **6.5. Differentiation Syndrome**

DS-1594b may result in terminal differentiation of leukemic blast cells in subjects with relapsed or refractory disease, which may be associated with the development of differentiation syndrome (also known as retinoic acid syndrome) and may be life-threatening or fatal if not treated.

It is important to promptly recognize the signs and symptoms of differentiation syndrome and implement appropriate treatment. Symptoms of differentiation syndrome could include dyspnea, unexplained fever, peripheral edema, unexplained hypotension, weight gain >5 kg, pulmonary

infiltrates, pleuro-pericardial effusion, acute renal failure, musculoskeletal pain, and hyperbilirubinemia. Less commonly, differentiation syndrome might present with pulmonary hemorrhage or acute febrile neutrophilic dermatosis.

The diagnosis of differentiation syndrome requires the presence of at least 2 of the following signs or symptoms: dyspnea, unexplained fever  $\geq 38^{\circ}\text{C}$ , weight gain  $> 5\text{ kg}$ , unexplained hypotension, acute renal failure, or a chest radiograph demonstrating pulmonary infiltrates or pleuro-pericardial effusion or multiple organ dysfunction. No single sign or symptom is sufficient to make a diagnosis of the syndrome. It is important to rule out other conditions with similar symptoms, such as sepsis, pneumonia, heart failure, pulmonary embolism, and diffuse alveolar hemorrhage.

For subjects at an increased risk for severe differentiation syndrome (white blood cell count  $> 5 \times 10^9/\text{L}$  or serum creatinine  $> 1.4\text{ mg/dL}$ ), consider the administration of prophylactic systemic glucocorticoids. For subjects with a white blood cell count  $> 10 \times 10^9/\text{L}$ , administer hydroxyurea 1-3g per day.

Subjects with suspected differentiation syndrome should promptly start treatment with intravenous or oral dexamethasone 10 mg every 12 hours or equivalent and hemodynamic monitoring until improvement. If symptoms do not improve after 24 hours of therapy, increase dexamethasone dosing to 10 mg every 6 hours. If severe pulmonary symptoms (requiring intubation or ventilatory support), and/or renal dysfunction persisting more than 48 hours after initiation of steroids, interrupt DS-1594b until signs and symptoms no longer severe (Table 13). Hospitalization for subjects with severe pulmonary or renal manifestation is recommended.

Formatted: C-Hyperlink

